11.8.2 Study Records Retention

Study documents should be retained for a minimum of 2 years after the last approval of a marketing application in an International Conference on Harmonisation (ICH) region and until there are no pending or contemplated marketing applications in an ICH region or until at least 2 years have elapsed since the formal discontinuation of clinical development of the study intervention, and as per the NIH Intramural Records Retention Schedule. No records will be destroyed without the written consent of the sponsor, if applicable. It is the responsibility of the sponsor to inform the investigator when these documents no longer need to be retained.

11.9 PROTOCOL DEVIATIONS AND NON-COMPLIANCE

It is the responsibility of the investigator to use continuous vigilance to identify and report deviations and/or non-compliance to FMPOS. The investigator is responsible for knowing and adhering to the reviewing IRB requirements.

11.9.1 Definition of Protocol Deviation

A protocol deviation is any changed, divergence, or departure from the IRB-approved research protocol.

- Major deviations: Deviations from the IRB approved protocol that have, or may have the potential to, negatively impact the rights, welfare or safety of the subject, or to substantially negatively impact the scientific integrity or validity of the study.
- Minor deviations: Deviations that do not have the potential to negatively impact the rights, safety or welfare of subjects or others, or the scientific integrity or validity of the study.

11.10 PUBLICATION AND DATA SHARING POLICY

11.10.1 Human Data Sharing Plan

This study will be conducted in accordance with the following publication and data sharing policies and regulations:

National Institutes of Health (NIH) Public Access Policy, which ensures that the public has access to the published results of NIH funded research. It requires scientists to submit final peer-reviewed journal manuscripts that arise from NIH funds to the digital archive [PubMed Central](#) upon acceptance for publication.

This study will comply with the NIH Data Sharing Policy and Policy on the Dissemination of NIH-Funded Clinical Trial Information and the Clinical Trials Registration and Results Information Submission rule. As such, this trial will be registered at ClinicalTrials.gov, and results information from this trial will be submitted to ClinicalTrials.gov. In addition, every attempt will be made to publish results in peer-reviewed journals.

11.10.2 Genomic Data Sharing Plan

This study will comply with the NIH Genomic Data Sharing Policy, which applies to all NIH-funded research that generates large-scale human or non-human genomic data, as well as the use of these data for subsequent research. Large-scale data include genome-wide association studies (GWAS), single nucleotide polymorphisms (SNP) arrays, and genome sequence, transcriptomic, epigenomic, and gene expression data.

Appendix A: Toxicity Tables for Children

Local Reactogenicity Grading¹

Local Reaction to	Mild	Moderate	Severe	Potentially Life
-------------------	------	----------	--------	------------------

Injectable Product	(Grade 1)	(Grade 2)	(Grade 3)	Threatening (Grade 4)
Pain at site	Does not interfere with activity	Repeated use of non-narcotic pain reliever > 24 hours or interferes with activity	Any use of narcotic pain reliever or prevents daily activity	ER visit or hospitalization
Erythema/Redness at site²	≤ 2.5 cm in diameter	> 2.5 cm in diameter with < 50% surface area of the extremity segment involved (e.g., upper arm or thigh)	≥ 50% surface area of the extremity segment involved (e.g., upper arm or thigh)	Potentially life-threatening consequences (e.g., abscess, exfoliative dermatitis, necrosis involving dermis or deeper tissue)
Induration/Swelling at site³	≤ 2.5 cm in diameter	> 2.5 cm in diameter with < 50% surface area of the extremity segment involved (e.g., upper arm or thigh)	≥ 50% surface area of the extremity segment involved (e.g., upper arm or thigh)	Potentially life-threatening consequences (e.g., abscess, exfoliative dermatitis, necrosis involving dermis or deeper tissue)
Bruising at site²	≤ 2.5 cm in diameter	> 2.5 cm in diameter with < 50% surface area of the extremity segment involved (e.g., upper arm or thigh)	≥ 50% surface area of the extremity segment involved (e.g., upper arm or thigh)	Potentially life-threatening consequences (e.g., abscess, exfoliative dermatitis, necrosis involving dermis or deeper tissue)
Pruritus at Site	Does not interfere with activity	Repeated use of medication > 24 hours or interferes with activity	Prevents daily activity	ER visit or hospitalization
Limitation of Arm Movement	Does not interfere with activity	Repeated use of medication > 24 hours or interferes with activity	Prevents daily activity	ER visit or hospitalization

Abbreviations: ER, emergency room.

¹ The definitions provided in the table are modified versions taken from the FDA Guidance for Industry “Toxicity Grading Scale for Healthy Adults and Adolescent Volunteers Enrolled in Preventive Vaccine Clinical Trials” dated September 2007 and DAIDS Table for Grading the Severity of Adult and Pediatric Adverse Events version 2.1 July 2017.

² In addition to grading the measured local reaction at the greatest single diameter, the measurement should be recorded as a continuous variable.

³ Induration/Swelling should be evaluated and graded using the functional scale as well as the actual measurement.

Vital Sign AE Grading¹

Vital Signs²	Mild (Grade 1)	Moderate (Grade 2)	Severe (Grade 3)	Potentially Life Threatening (Grade 4)
Fever³ (°C) (°F)	37.5 – 38.4 100.4 – 101.1	38.5 – 38.9 101.2 – 102.0	39.0 – 40 102.1 – 104	> 40 > 104
Tachycardia - beats per minute; at rest + calm	121 – 135	136 – 150	>150	ER visit or hospitalization for arrhythmia
Bradycardia - beats per minute ⁴ ; at rest + calm	55 – 59	50 – 54	< 50	ER visit or hospitalization for arrhythmia
Hypertension - mm Hg; at rest + calm	NA	91st – 94th percentile adjusted for age, height, and gender (systolic and/or diastolic)	≥ 95th percentile adjusted for age, height, and gender (systolic and/or diastolic)	ER visit or hospitalization for malignant hypertension
Hypotension (systolic) - mm Hg; at rest + calm	NA	Symptomatic, corrected with oral fluid replacement	Symptomatic, IV fluids indicated	ER visit or hospitalization for hypotensive shock

Abbreviations: ER, emergency room.

¹ The definitions provided in the table are taken from the FDA Guidance for Industry “Toxicity Grading Scale for Healthy Adults and Adolescent Volunteers Enrolled in Preventive Vaccine Clinical Trials” dated September 2007 and the “Division of AIDS Table for Grading the Severity of Adult and Pediatric Adverse Events” Version 1.0, December 2004, Clarification August 2009.

² Subject should be at rest for all vital sign measurements.

³ Oral temperature; no recent hot or cold beverages or smoking.

⁴ When resting heart rate is between 60 – 100 beats per minute

Systemic AE Grading¹

Systemic AEs	Mild (Grade 1)	Moderate (Grade 2)	Severe (Grade 3)	Potentially Life Threatening (Grade 4)
Diarrhea	2 – 3 loose stools or < 400 gms/24 hours	4 – 5 stools or 400 – 800 gms/24 hours	6 or more watery stools or > 800 gms/24 hours or requires outpatient IV hydration	ER visit or hospitalization
Headache	No interference with activity	Repeated use of non-narcotic pain reliever > 24 hours or some interference with activity	Significant; any use of narcotic pain reliever or prevents daily activity	ER visit or hospitalization
Malaise	No interference with activity	Some interference with activity	Significant; prevents daily activity	ER visit or hospitalization
Myalgia	No interference with activity	Some interference with activity	Significant; prevents daily activity	ER visit or hospitalization
Arthralgia	No interference with activity	Some interference with activity	Significant; prevents daily activity	ER visit or hospitalization
Nausea/ Vomiting	No interference with activity or 1 – 2 episodes/24 hours	Some interference with activity or > 2 episodes/24 hours	Prevents daily activity, requires outpatient IV hydration	ER visit or hospitalization for hypotensive shock
Seizures- includes new or pre-existing febrile seizures	NA	NA	Seizure(s) that are not prolonged or repetitive	Prolonged and repetitive seizures (e.g., status epilepticus) OR Difficult to control (e.g., refractory epilepsy)

Abbreviations: ER, emergency room; IV, intravenous; PO, “per os” or oral administration.

¹ The definitions provided in the table are modified versions taken from the FDA Guidance for Industry “Toxicity Grading Scale for Healthy Adults and Adolescent Volunteers Enrolled in Preventive Vaccine Clinical Trials” dated September 2007 and DAIDS Table for Grading the Severity of Adult and Pediatric Adverse Events version 2.1 July 2017.

Mali Laboratory AE Grading for Pediatric Population

Hematology and Biochemistry Values ^{1, 2}	Mild (Grade 1)	Moderate (Grade 2)	Severe (Grade 3)	Potentially Life Threatening (Grade 4)
Hemoglobin (Male/Female) - gm/dL	7.5 – 8.4	6.1 – 7.4	5.0 – 6.0	< 5.0 g/dL
WBC Increase - 10³/µL	14.5 – 16.0	16.1 – 20.0	20.1 – 30.0	>30.0
WBC Decrease - 10³/µL	2.5 – 3.3	1.5 – 2.4	1.0 – 1.4	< 1.0 with or without fever
Neutrophil/Granulocyte Decrease³ - 10³/µL	0.75 – 0.99	0.50 – 0.74	< 0.50	< 0.50 with fever
Platelets Decreased - 10³/µL	100 – 120	70 – 99	25 – 69	< 25
Creatinine (Male/Female) - µmol/L	95.00 – 119.99	120.00 – 149.99	150.00 – 200.00	> 200.00 and requires dialysis
Liver Function Tests/ALT - U/L	75.0 – 150.9	151.0 – 300.9	301.0 – 600.0	> 600.0

Abbreviations: ALT, alanine transaminase; WBC, white blood cell.

¹ The laboratory values provided in the tables serve as guidelines and are dependent upon institutional normal parameters. Institutional normal reference ranges should be provided to demonstrate that they are appropriate.

² The clinical signs or symptoms associated with laboratory abnormalities might result in characterization of the laboratory abnormalities as Potentially Life Threatening (Grade 4). For example, a low sodium value that falls within a grade 3 parameter should be recorded as a grade 4 hyponatremia event if the subject had a new seizure associated with the low sodium value.

³ Note, neutropenias are graded and followed, but based on previous experience in African populations, should be interpreted with caution since lower values are more frequently observed in people of African descent. ([38](#), [39](#))

Appendix B: Institutional Normal Laboratory Values for Children

Hematology Reference Intervals*

	Reference Interval	Units
WBC- Leukocytes	4.8 – 11.2	$10^3/\mu\text{L}$
Hemoglobin	9.1 – 13.3	g/dL
Platelet Count	188 – 551	$10^3/\mu\text{L}$
Absolute Granulocyte Count	1.4 – 5.9	$10^3/\mu\text{L}$

*Based on children ranging in age from 5 to 9 years old (based on sampling done at Bancoumana and Doneguebougou research sites, Mali)

Biochemistry Reference Intervals*

	Reference Interval	Units
ALT	11.5 – 53.0	U/L
Creatinine	< 80.6	$\mu\text{M/L}$

*Based on children ranging in age from 5 to 9 years old (based on sampling done at Bancoumana and Doneguebougou research sites, Mali)

Statistical analysis plan for

Phase 2 Trial of Safety, Immunogenicity, and Efficacy against *Plasmodium falciparum* Malaria of PfSPZ Vaccine in Children in Mali

1. Populations for Analyses

The following analysis populations will be used when describing subject disposition and performing statistical analyses:

- The **Screened Population** includes all subjects who are screened and provide informed consent, regardless of whether the subject is randomized or treated. This population will be used to fully account for subject disposition.
- The **Intention to Treat (ITT) Population** is a subset of the screened population that is deemed eligible to participate in the study, is randomized to a treatment group, receives *at least one injection* with PfSPZ Vaccine or placebo, and contributes evaluable person-time to the risk set.
- The **Modified Intention to Treat (mITT) Population** includes all subjects who are deemed eligible to participate, are randomized, receive *all three injections* of vaccine or placebo, and contribute evaluable person-time to the risk set, including subjects to whom V2 and/or V3 is administered out of the pre-specified time window or an incomplete injection is given, defined as an estimated injection volume of at least 10% and less than 80%.
- The **According to Protocol (ATP) Population** is a subset of the mITT Population, including subjects who complete the vaccination series per protocol and contribute evaluable person-time to the risk set.

2. Study endpoints

2.1 Safety endpoints

The primary safety endpoint is the proportion of vaccinees experiencing related SAEs from V1 to 26 weeks after V3.

The secondary safety endpoints include the occurrence of unsolicited AEs, laboratory abnormalities, and solicited AEs in the ITT population.

2.2 Efficacy endpoints

The primary efficacy endpoint is the vaccine efficacy against *malaria with symptoms* detected by TBS. TBS are deemed positive if at least one unambiguous asexual blood stage parasite is identified by two independent microscopists after each examining 0.50

μL of blood. For this protocol, there is a primary and a secondary case definition of Pf *malaria with symptoms*.

Primary case definition:

Pf *malaria with symptoms* is defined as a positive thick blood smear at a density of >1000 parasites/ μL (P/ μL) plus:

- Measured fever ≥ 37.5 degrees Celsius or history of fever (subjective or objective) in the last 24 hours, or,
- Symptoms of malaria:
 - Verbal individual (individual able and willing to answer questions): A verbal individual is considered symptomatic if reporting at the time of evaluation at least two of the following symptoms/symptom groups: headache, chills and/or rigors, malaise and/or fatigue, dizziness and/or light-headedness, myalgias and/or arthralgias; or
 - Non-verbal individual (small child or any individual unable or unwilling to answer questions): A non-verbal individual is considered symptomatic if manifesting at the time of evaluation at least two of the following signs/sign groups: drowsiness, irritability and/or fussiness, inability and/or refusal to eat or drink, prostration; or
- Any individual: Signs of severe malaria.

Secondary case definition:

Pf *malaria with symptoms* is defined as a positive thick blood smear at a density of > 0 P/ μL plus:

- Measured axillary temperature ≥ 37.5 degrees Celsius or history of fever (subjective or objective) in the last 24 hours, or,
- Symptoms of malaria as defined in the primary case definition; or
- Meeting criteria for severe malaria

The secondary efficacy endpoint is the vaccine efficacy against Pf malaria.

Pf *malaria* is defined as:

- At least one unambiguous asexual parasite on thick blood smear identified by two independent microscopists after each examining $0.50 \mu\text{L}$ of blood in a study participant

3. Analysis methods

3.1 Safety Analyses

The primary safety endpoint is the occurrence of an SAE between V1 and 26 weeks after V3 which is at least possibly related to treatment. Serious AEs which meet this definition will be summarized in frequency tables and listings according to system organ class, preferred term, relatedness, and severity. The primary safety analysis will be performed using the ITT population and according to treatment received at V1, regardless of any randomization or allocation errors. All SAEs will be coded using the Medical Dictionary for Regulatory Activities (MedDRA) and summarized using frequencies, proportions, and exact 95% CIs for proportions. Rates of SAEs (overall and for any system organ class or preferred term with at least 5 events in either group) will be compared using two-sided 0.05 level Fisher's Exact Tests.

Secondary safety endpoints include the occurrence of unsolicited AEs, laboratory abnormalities, and solicited AEs in the ITT population. Unsolicited AEs documented from V1 to 14 days following V3 will be coded using MedDRA and summarized in frequency tables according to system organ class, preferred term, relatedness, and severity. Summaries will be provided overall and according to the vaccination number immediately prior to AE onset. Rates of unsolicited AEs (overall and for any system organ class or preferred term with at least 5 events in either group) will be compared using two-sided 0.05 level Fisher's Exact Tests. Adverse events leading to premature discontinuation from the study will be listed separately. Clinically relevant laboratory abnormalities recorded in the 14 days after V3 will be summarized in frequency tables by type, grade, and clinical relevance.

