7.3 MEASURES TO MINIMIZE BIAS: RANDOMIZATION AND BLINDING

7.3.1 Randomization

Randomization will occur in blocks at 1:1 into vaccine or placebo arms. Randomization will be assigned at the time of first artemether/lumefantrine dose with the next available subject. Once a subject has received their first vaccination, they cannot be replaced.

During the study, the list linking randomization numbers to study product (PfSPZ Vaccine or control) will be made available only to the study statistician and associated team members, pharmaceutical operations team/syringe preparers (at the start of the study), independent safety monitor (if needed to review), and DSMB chair (if needed for closed session unblinded review). On vaccination days, the vaccines associated with each randomization number will be obtained from the head of pharmaceutical operations.

If a subject is given the wrong treatment at V1 due to an allocation error, the same vaccine will be administered at V2 and V3 so long as the error is identified before the timing of the next injection. In the situation where an eligible participant already assigned a randomization number becomes ineligible during the window between randomization number assignment and administration of V1 (e.g., as a result of new information about the participant, withdrawal from participation, or other factors), a replacement will not be assigned, and the randomization number will not be assigned to another participant. This occurrence is anticipated to be a rare event.

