7.3.3 Unblinding

Details of unblinding procedures are provided in the unblinding SOP. An overview is provided here.

Unblinding of individual participants: If knowledge of the treatment assignment is needed to provide appropriate medical care, and unblinding is recommended by the principal investigator, the local safety monitor (LSM), or the DSMB, the treatment assignment of that research subject may be unblinded and provided to the treating clinician and other clinical staff on a need-to-know basis by the head of Pharmaceutical Operations at the study site or other designated unblinded staff who have access to the unblinded randomization list and pharmaceutical team records. The principal investigator must contact the Sponsor and provide documentation of the event and the reasons for unblinding.

If pausing criteria are met based on blinded data, the following procedure will be followed, as described in **Section 7.1.1**. The principal investigator (who remains blinded) will provide the list of research subjects contributing to pausing criteria to the head of Pharmaceutical Operations or their designee, and will also inform the head of Pharmaceutical Operations how many of these research subjects have to be vaccine recipients (as opposed to NS recipients) in order to know if pausing criteria have truly been met. The head of Pharmaceutical Operations will then privately identify the treatment assignment of each participant on the list, and then inform the principal investigator if the pausing criteria have been met, but will not unblind the principal investigator with respect to individual participants.

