- Five percent or more of the vaccinees enrolled at any time point in one arm (calculated as 5% of the vaccinees in the full study roster enrolled to date, as long as there are at least three subjects with the AE) experience the same severe (grade 3) AE during the periods of AE collection deemed possibly, probably or definitely related to study product administration (PfSPZ Vaccine or NS), or experience the same grade 3 laboratory abnormality on day V2 + 14 or day V3+14. Grade 3 AEs deemed possibly, probably or definitely related to malaria (as opposed to PfSPZ Vaccine or to NS) will not count toward meeting this criterion. The site, where clinical staff are blinded, can only monitor total populations (vaccine plus placebo recipients) and if a 5% threshold is reached, unblinded study staff (e.g., the head of Pharmaceutical Operations) will need to confirm that the total indeed constitutes 5% of vaccinees. Note that we have considered using Grade 2 rather than Grade 3 laboratory abnormalities, but drops in hemoglobin, neutrophils, platelets and sometimes other blood count indices meeting Grade 2 criteria for severity are common in African pediatric populations.
- One participant experiences an SAE deemed possibly, probably or definitely related to study product. This criterion will not be met if it turns out that the participant received NS. SAEs related to malaria or to antimalarial treatment which are expected, will be reported expeditiously but will not fulfill this criterion. If the SAE is unexpected with respect to malaria or antimalarial treatment, it will fulfill the criterion.

If either of these criteria appear to be met by ongoing surveillance at the site, the principal investigator will engage the head of Pharmaceutical Operations on site, or his/her designee, to

follow unblinding procedures (see **Section 6.3.3** for a description). To meet the criteria, the subjects must actually have received PfSPZ Vaccine and not NS placebo.

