10.1 STATISTICAL HYPOTHESIS

Primary Endpoints

Safety: The primary safety endpoint is the proportion of vaccinees experiencing related SAEs from V1 to 26 weeks after V3. There is no formal hypothesis test associated with this primary safety endpoint. Rather, the proportion of subjects experiencing related SAEs will be presented for each arm separately using frequencies, percentages, and descriptive 95% confidence intervals (CIs).

Efficacy: the primary efficacy endpoint is the vaccine efficacy against *malaria with symptoms*. For this protocol, there is a primary and a secondary case definition of *Pf malaria with symptoms*.

The primary case definition is as follows:

Pf malaria with symptoms is defined as a positive thick blood smear at a density of >1000 P/uL plus:

- Measured axillary temperature ≥ 37.5 degrees Celsius or history of fever (subjective or objective) in the last 24 hours, or,
- Symptoms of malaria –
 - Verbal individual (individual able and willing to answer questions): A verbal individual is considered symptomatic if reporting at the time of evaluation at least two of the following symptoms/symptom groups: headache, chills and/or rigors, malaise and/or fatigue, dizziness and/or light-headedness, myalgias and/or arthralgias; or
 - Non-verbal individual (small child or any individual unable or unwilling to answer questions): A non-verbal individual is considered symptomatic if manifesting at the time of evaluation at least two of the following signs/sign groups: drowsiness, irritability and/or fussiness, inability and/or refusal to eat or drink, prostration; or
- Any individual: Signs of severe malaria (e.g. impairment of consciousness, severe anemia, hemoglobinuria, acute kidney injury, etc.).

The secondary case definition is as follows:

Pf malaria with symptoms is defined as a positive thick blood smear at a density of > 0 P/uL plus:

- Measured axillary temperature ≥ 37.5 degrees Celsius or history of fever (subjective or objective) in the last 24 hours, or,
- Symptoms of malaria as defined in the primary case definition; or
- Meeting criteria for severe malaria

The formal hypothesis associated with the primary efficacy endpoint is a superiority test of

$$H_0: VE = 0 \text{ versus } H_A: VE < > 0$$

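### The primary safety analysis classes each child by the product received at V1, so a child given saline at V1 and PfSPZ Vaccine at a later dose, which the error rule does not wholly prevent, has vaccine-exposed SAEs counted as placebo

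*SAP*

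**What the plan says.** SAP 3.1 defines the endpoint and its window: "The primary safety endpoint is the occurrence of an SAE between V1 and 26 weeks after V3", restricted to events at least possibly related to treatment. The analysis uses the ITT population (at least one injection) and groups children "according to treatment received at V1, regardless of any randomization or allocation errors". Protocol 10.4.2 has the same rule.

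Protocol 7.3.1 covers one kind of dosing error. It begins "If a subject is given the wrong treatment at V1 due to an allocation error" and continues that "the same vaccine will be administered at V2 and V3 so long as the error is identified before the timing of the next injection". It does not cover a V1 error found after that point, or an error that first occurs at V2 or V3. Neither document says how to class a child who received both products.

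On inference, protocol 10.1 states: "There is no formal hypothesis test associated with this primary safety endpoint". Protocol 10.4.2 and SAP 3.1 nevertheless say that SAE rates "will be compared using two-sided 0.05 level" Fisher's exact tests.

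For the pausing check, protocol 7.3.3 has the head of Pharmaceutical Operations, who "will then privately identify the treatment assignment of each participant on the list". The section headed Pausing Criteria, Unblinding and Safety Hold (within 8.1) says: "To meet the criteria, the subjects must actually have received PfSPZ Vaccine and not NS placebo".

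**The concern.** The grouping variable is fixed at the first of three injections, while events are counted after all three. For a child who received saline first and PfSPZ Vaccine later, every vaccine exposure comes after the moment that decides the group. A related SAE in that child would appear in the saline column, which understates risk in the vaccine group and overstates it in the control group.

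The protocol itself expects few related SAEs, so a single event can change what the primary safety table shows. The background to the pausing criteria also notes that this is only the second paediatric study with two doses one week apart, and stresses safety follow-up after the second dose. A V1-only rule ignores that exposure when the first dose was saline.

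**Working it through.** **Which dosing sequences are affected**

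| Sequence | Class under V1 rule | Class by any PfSPZ received | Differs? |
|---|---|---|---|
| Wrong product at V1, found in time, same product continued (7.3.1) | product received throughout | same | no |
| PfSPZ at V1, saline at a later dose | vaccine | vaccine | no |
| Saline at V1 in error, found late, PfSPZ at V2 and/or V3 | placebo | vaccine | yes |
| Saline at V1 as assigned, PfSPZ in error at V2 or V3 | placebo | vaccine | yes |

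Only the last two rows matter. The Schedule of Activities puts V2 on Day 8 with a window of -1/+3 days. A V1 error therefore has to be found within about 6 to 10 days for the 7.3.1 safeguard to work.

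**Reproducing the plan's own precision figure**

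Protocol 10.2 gives an upper bound of 0.030 for 0/120. The exact (Clopper-Pearson) upper limit for 0/n is 1 − 0.025^(1/n). For n = 120 this is 0.0303, which agrees.

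**Effect of one child**

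Inputs: about 134 per arm (protocol 10.2). Assumptions: all of these children are in the ITT population, one child has mixed exposure, that child has one related SAE after PfSPZ, and there are no other related SAEs.

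Formulas: for 0/n, the upper limit is 1 − 0.025^(1/n). For 1/n, the lower limit is 1 − 0.975^(1/n) and the upper limit is the 97.5th percentile of Beta(2, n − 1).

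Case A, vaccine-assigned child given saline at V1 and PfSPZ later:

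- V1 rule: vaccine 0/133 (0 to 2.7%); saline 1/135 (0.02% to 4.1%).
- Any-PfSPZ rule: vaccine 1/134 (0.02% to 4.1%); saline 0/134 (0 to 2.7%).

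Case B, placebo-assigned child given PfSPZ in error at V2 or V3:

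- V1 rule: vaccine 0/134 (0 to 2.7%); saline 1/134 (0.02% to 4.1%).
- Any-PfSPZ rule: vaccine 1/135 (0.02% to 4.1%); saline 0/133 (0 to 2.7%).

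The denominator moves with the child, so the arm sizes differ between the two rules.

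**Effect on the Fisher comparison (Case A)**

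With one SAE, p = 1.0 under either rule. With six related SAEs in total, a count assumed purely for illustration, 6/134 against 0/134 gives p = 0.030. Under the V1 rule the same data become 5/133 against 1/135, with p = 0.119.

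**The case against.** The strongest reply is that the protocol has already dealt with the main case. A V1 error found in time leaves the child on one product, and the V1 class is then right. A reader might infer that every misallocated child is misfiled; 7.3.1 shows that this is not so. Protocol 7.2.1 requires preparation and injection each to be signed and verified, which should make errors uncommon. The endpoint is descriptive, one event leaves the Fisher p-value at 1.0, and related SAEs are to be listed as well as tabulated.

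Most of this stands, and it limits the size of the point. It does not remove it. For a child with saline first and PfSPZ later, the stated rule gives the wrong group. The listings are described by system organ class, preferred term, relatedness and severity; nothing says they will show the product given at each injection.

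A reader might also infer that, because 7.3.3 speaks of assignment, a related SAE in a placebo-assigned child who actually received PfSPZ would be reported as not meeting the pausing criterion. The documents do not support that. Section 7.3.3 calls itself an overview of a separate SOP and itself refers to vaccine recipients as opposed to saline recipients. The pausing section states the as-received standard twice. Section 8.1 also allows a pause irrespective of the criteria, and 11.5 sends all related SAEs to the DSMB without restriction by arm. What remains is a difference in wording.

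**Conclusion.** The point holds in a narrow form. The V1 rule misclassifies children whose first injection was saline and who later received PfSPZ Vaccine, and no others. This can happen only if a V1 error is found too late or a separate error occurs at V2 or V3. The documents give no allocation-error rate, so the expected number of such children cannot be estimated; it should be small.

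Where it happens, the bias is in the unfavourable direction for a safety analysis: one related SAE turns an observed vaccine count of 1 into 0 and puts a 1 in the saline group. The effect is mainly on the per-arm proportions and intervals. The change in significance shown above depends on an assumed six related SAEs. The pausing text supports no more than a request to reconcile two passages.

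**What to change.** In SAP 3.1 and protocol 10.4.2, replace the V1 rule with: *children who received at least one injection of PfSPZ Vaccine are analysed in the vaccine group; only children who received saline at every injection are analysed as placebo.* Each child then has one group and one denominator, as a per-child proportion needs. List the mixed-exposure children with the product given at each injection, and flag any SAE that began before the first PfSPZ dose.

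Reconcile protocol 7.3.3 with the Pausing Criteria section, so that both describe the product check for a misallocated child in the same terms.

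The cost is wording only. Protocol 7.2.1 already requires injection-level product records. Children who received one product throughout keep their class. The small downside is that an SAE before the first PfSPZ dose in a mixed-exposure child counts in the vaccine group; this is conservative, and the flag makes it visible. The change should be made before unblinding, so that no child's group is decided after an event is known.
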